5.2. Study Drugs

5.2.1. Ruxolitinib

5.2.1.1. Description and Administration

Ruxolitinib 5 mg tablets are round and white to off-white in color.

Subjects will begin treatment at ruxolitinib 5 mg BID; if hematologic parameters are stable and no treatment-related toxicity is observed after the first 3 days of treatment, the dose may be increased to 10 mg BID. Stable hematologic parameters are defined as the absence of $a \ge 50\%$ decrease in platelet counts and/or ANC relative to Day 1. Ruxolitinib may be taken without regard to food except on days when PK samples are drawn; on those days, subjects should be instructed to fast and refrain from taking ruxolitinib until PK samples are collected. See Section 7.7.1 for additional information.

Subjects may have dose reductions or modifications of ruxolitinib during the course of treatment based on AEs, clinical evaluation, and laboratory assessments. See Section 5.4.1 for dose modifications of ruxolitinib.

Subjects are permitted to remain on ruxolitinib treatment until withdrawal from study treatment is considered necessary as per Section 5.5.

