Hepatitis screening	7.5.6.4	Х		•													
Serum pregnancy test (childbearing females only)	7.5.6.3	х										х					
Urine pregnancy test ^e (childbearing females only)	7.5.6.3			х													
PK assessment ^f	7.7		х		Х	Х											
Correlative study blood collection	7.8	х	x		х	х		х				\mathbf{X}^{g}	х	х	х	х	

^a A ± 2-day window is permitted to facilitate scheduling during the treatment phase.
 ^b Day 1 laboratory assessments do not need to be repeated if screening assessments were performed in preceding 7 days.
 ^c After Day 56, visits will occur every 28 days and will include all Day 56 assessments.

^d The Day 365 visit will also serve as the regularly scheduled visit occurring every 28 days after Day 56 (ie, Day 364).

* Urine pregnancy tests are only required if medically indicated and should be confirmed with a serum pregnancy test.

^f Samples to be collected at predose and at 1 hour \pm 15 minutes, at 2 hours \pm 30 minutes, and between 4 and 8 hours postdose. ^g Day 56 only.

Serum Chemistries	Hematology ^a	Other
Albumin	Hematocrit	Serum pregnancy test
ALP	Hemoglobin	Urine pregnancy test ^b
ALT	Mean corpuscular volume	
AST	Platelet count	
Bicarbonate	Red blood cell count	
Blood urea nitrogen	Reticulocyte count	
Calcium	White blood cell count	
Chloride	White blood cell differential (5 parts):	Hepatitis Screening Tests
Creatinine	Basophils	
Glucose	• Eosinophils	Hepatitis B surface antigen
Lactate dehydrogenase	• Lymphocytes	Hepatitis B surface antigen antibody
Phosphorus	Monocytes	Hepatitis B core antibody
Potassium	Neutrophils	Hepatitis C virus antibody
Sodium	·······	HCV-RNA
Total bilirubin		HEV-KNA HBV-DNA
Total protein		

 Table 7:
 Clinical Laboratory Analytes

ALP = alkaline phosphatase.

^a Hematology and chemistry assessments will be performed locally.

^b Urine pregnancy tests are only required if medically indicated.

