6.1. Screening

The screening period is the interval between signing the ICF and the day that the subject is enrolled in the study (Day 1). The screening period may not exceed 28 days. Informed consent must be obtained before performing any study-specific procedures that are not considered standard of care. Assessments that are required to demonstrate eligibility may be performed over the course of 1 or more days during this period.

Procedures conducted as part of the subject's routine clinical management (eg, blood count, imaging study) and obtained before signing the ICF may be used for screening or baseline purposes, provided that the procedure meets the Protocol-defined criteria and has been performed in the timeframe of the study. Results from the screening visit evaluations will be reviewed to confirm subject eligibility before enrollment or the administration of study drug. Tests with results that fail eligibility requirements may be repeated once during the screening period if the investigator believes the results to be in error. For screening assessments that are repeated, the most recent available result before enrollment will be used to determine subject eligibility. Treatment should start as soon as possible, but within 2 days after the date of enrollment. Additionally, a subject who fails screening may repeat the screening process 1 time if the investigator believes that there has been a change in eligibility status (eg, following recovery from an infection).

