7.6. Graft-Versus-Host Disease Assessments

7.6.1. Graft-Versus-Host Disease Staging and Grading

Acute GVHD grading will be performed by the investigator on a weekly basis for the first 8 weeks after enrollment, then every 28 days thereafter. Graft-versus-host disease staging and grading will also occur on Days 100, 180, and 365 and at the EOT visit. If subjects withdrew due to reasons other than GVHD progression, then GVHD staging and grading will be assessed at the safety follow-up visit. Data regarding the quantification of aGVHD symptoms (extent of skin rash, total bilirubin level, volume of diarrhea) should be reported using MAGIC guidelines (Harris et al 2016); response will be assessed as per the Center for International Blood and Marrow Transplant Research (CIBMTR) modifications to the IBMTR response index as indicated in Appendix B (CIBMTR 2009, Martin et al 2009).

- Skin:
 - Only areas involved with active erythema should be used for determining body surface area staging based on the rule of nines.
 - A portion of a body area segment may be used for the quantification.
 - Desquamation or fluid-filled bullae should be reported if present as these findings are hallmarks of Stage 4 skin GVHD.
- Liver:
 - Liver GVHD staging is based solely on total (not conjugated/direct) serum bilirubin levels.
 - Liver GVHD manifesting as transaminitis without concomitant elevation in serum bilirubin should be diagnosed when the presence of GVHD is confirmed by liver biopsy (where appropriate) and scored as Stage 0.
 - If bilirubin levels were elevated before the diagnosis of GVHD in another target organ and do not increase further, then liver GVHD should not be diagnosed in the absence of biopsy confirmation. However, if hyperbilirubinemia develops at the same time or after the onset of GVHD in another target organ, then liver GVHD is presumed to be present in the absence of an identified alternative cause.

- Upper GI:
 - Symptoms of concern for upper GI GVHD include anorexia, nausea, vomiting, and dyspepsia, and assessment depends on close attention to caloric intake and symptom reporting.
 - An upper GI endoscopy should be performed whenever possible to confirm upper GI GVHD; however, the diagnosis may be made without biopsy confirmation.
 - Graft-versus-host disease is typically not considered as a possible etiology when nausea lasts fewer than 3 days or with fewer than 2 vomiting episodes per day for at least 2 days or anorexia without weight loss.

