9.4. Statistical Analyses

9.4.1. Primary Analyses

The primary endpoint is ORR at Day 28, defined as the proportion of subjects demonstrating a CR, VGPR, or PR, as per standard criteria (Appendix B). The primary analysis will be conducted once the last subject completes the Day 28 visit or withdraws from the study.

Summary statistics and 95% CI will be provided.

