Appendix B. MAGIC GUIDELINES FOR STAGING AND GRADING ACUTE GVHD

Stage	Skin (Active Erythema Only)	Liver (Bilirubin)	Upper GI	Lower GI (Stool Output/Day)
0	No active (erythematous) GVHD rash	< 2 mg/dL	No or intermittent nausea, vomiting, or anorexia	Adult: < 500 mL/day or < 3 episodes/day. Child: < 10 mL/kg per day or < 4 episodes/day.
1	Maculopapular rash < 25% BSA	2-3 mg/dL	Persistent nausea, vomiting, or anorexia	Adult: 500-999 mL/day or 3-4 episodes/day. Child: 10-19.9 mL/kg per day or 4-6 episodes/day.
2	Maculopapular rash 25%-50% BSA	3.1-6 mg/dL	_	Adult: 1000-1500mL/day or 5-7 episodes/day. Child: 20-30 mL/kg per day or 7-10 episodes/day.
3	Maculopapular rash > 50% BSA	6.1-15 mg/dL	_	Adult: > 1500 mL/day or > 7 episodes/day. Child: > 30 mL/kg per day or > 10 episodes/day.
4	Generalized erythroderma (>50%) with bullae	> 15 mg/dL	_	Severe abdominal pain with or without ileus or grossly bloody stool (regardless of stool volume).

Acute GVHD Staging and Grading, MAGIC Guidelines

Overall clinical grade (based on most severe target organ involvement):

Grade 0: No stage 1-4 of any organ.

Grade I: Stage 1-2 skin without liver, upper GI, or lower GI involvement.

Grade II: Stage 3 rash and/or stage 1 liver and/or stage 1 upper GI and/or stage 1 lower GI.

Grade III: Stage 2-3 liver and/or stage 2-3 lower GI, with stage 0-3 skin and/or stage 0-1 upper GI.

Grade IV: Stage 4 skin, liver, or lower GI involvement, with stage 0-1 upper GI.

Response Definitions:

GVHD response assessments will be made with respect to changes in the organ stage relative to Study Day 1.

- Complete response (CR) is defined as a score of 0 for the GVHD grading in all evaluable organs. For a response to be scored as CR at Day 28 or later, the participant must still be in CR on that day and have had no intervening additional therapy for an earlier progression, mixed response (MR), or no response (NR).
- Very good partial response (VGPR) is defined as follows:
 - Skin: No rash, or residual erythematous rash involving < 25% of the body surface, without bullae (residual faint erythema and hyperpigmentation do not count).
 - Liver: Total serum bilirubin concentration < 2 mg/dL or < 25% of baseline at enrollment.
 - Gut:
 - Tolerating food or enteral feeding.
 - Predominantly formed stools.
 - o No overt gastrointestinal bleeding or abdominal cramping.
 - No more than occasional nausea or vomiting.

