- Partial response (PR) is defined as improvement in 1 stage in 1 or more organs involved with GVHD symptoms without progression in others. For a response to be scored as PR at Day 28 or later, the participant must still be in PR on that day and have had no intervening additional therapy for an earlier progression, MR, or NR.
- Mixed response is defined as improvement in 1 or more organs with deterioration in another organ manifesting symptoms of GVHD or development of symptoms of GVHD in a new organ.
- Progression of disease is defined as deterioration in at least 1 organ without any improvement in others.
- No response is defined as absence of any improvement or progression as defined. Subjects receiving secondary therapy (including need to re-escalate steroid dose to greater than the Day 1 dose) will be classified as nonresponders.

Source: CIBMTR 2009, Martin et al 2009, Harris et al 2016.

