4.1.3. Baseline Value

Baseline is the last nonmissing measurement obtained on or before the day of the first administration of study drug. When scheduled assessments and unscheduled assessments occur on the same day and time of the assessment or first dose is not available, use the following convention to determine baseline:

- If both a scheduled and an unscheduled visit are available on the day of the first dose and the time is missing, use the scheduled assessment as baseline.
- If all scheduled assessments are missing on the day of the first dose and an unscheduled assessment is available, use the unscheduled assessment as baseline.

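### The Day 1 laboratory waiver lets the liver baseline for response rest on a bilirubin up to 7 days old

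*Protocol*

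**What the plan says.** The point rests on provisions in several places.

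- **Reference point.** Protocol Appendix B, repeated in SAP Appendix B: "GVHD response assessments will be made with respect to changes in the organ stage relative to Study Day 1".
- **Liver input.** Protocol Section 7.6.1: "Liver GVHD staging is based solely on total (not conjugated/direct) serum bilirubin levels". Total bilirubin belongs to the chemistry panel (Table 7).
- **Smallest response that counts.** Appendix B: "Partial response (PR) is defined as improvement in 1 stage in 1 or more organs involved with GVHD symptoms without progression in others". A PR counts in the primary endpoint, ORR at Day 28 (Section 9.4.1).
- **Schedule.** Table 5 puts acute GVHD grading on Day 1, and Table 6 puts chemistry and hematology there.
- **Waiver.** Table 6 footnote b, and the same footnote in SAP Appendix C: "Day 1 laboratory assessments do not need to be repeated if screening assessments were performed in preceding 7 days". No analyte is excepted.
- **Baseline rule.** SAP Section 4.1.3: "Baseline is the last nonmissing measurement obtained on or before the day of the first administration of study drug". It sets no maximum age. Protocol Section 6.1 adds that routine-care results "obtained before signing the ICF may be used for screening or baseline purposes", provided they meet the protocol's criteria and timeframe.

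**The concern.** Skin and gut can be staged by examination and history at the Day 1 visit. The liver cannot be staged without a bilirubin, and the waiver removes the obligation to have one that day. A site that follows the protocol exactly can therefore record a Day 1 staging that joins same-day skin and gut stages to a liver stage up to a week old.

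Seven days is long by the protocol's own standard. Inclusion criterion 4a treats a rise in stage after 3 days of steroids as meaningful progression. Treatment-phase visits carry a window of only ±2 days, so the Day 28 end of the comparison is held more tightly than the baseline end.

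The study has a single cohort. Any bilirubin change between the screening draw and first dose is read as change on ruxolitinib, and no control arm would show the same drift. At stake is whether some liver-driven classifications in the primary endpoint describe what happened on drug.

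**Working it through.** **1. The plan's own figures.** The rule is to stop if 15 or fewer of 35 respond and otherwise to declare success at 37 or more of 70. Its exact probability of success at true rate p is the sum over x = 16 to 35 of P(X₁ = x) × P(X₂ ≥ 37 − x), where X₁ and X₂ are each binomial(35, p).

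- p = 0.40: 0.01888 (stated 0.0189).
- p = 0.60: 0.8988 (stated 89.88%).
- P(X₁ ≤ 15) at p = 0.40: 0.7003 (stated 70.03%).

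All three reproduce. This point disputes none of them, and the fix changes none of them.

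**2. Can the misclassification happen under the rules as written?** The Appendix B cut-offs for liver stage are below 2 mg/dL for Stage 0, 2–3 for Stage 1 and 3.1–6 for Stage 2. Both cases below are hypothetical. They assume that the waiver was used, that no bilirubin was recorded between the screening draw and first dose, and that no other organ improved or progressed.

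| Case | Screening, Day −7 | True Day 1 | Day 28 | Scored against screening | Scored against true Day 1 |
|---|---|---|---|---|---|
| (a) | 3.4 (Stage 2) | 2.9 (Stage 1) | 2.9 (Stage 1) | 2 → 1: PR | 1 → 1: no response |
| (b) | 1.9 (Stage 0) | 4.0 (Stage 2) | 2.5 (Stage 1) | 0 → 1: progression | 2 → 1: PR |

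Case (a) creates a responder and case (b) loses one. If another organ had improved in case (b), the recorded result would be a mixed response instead of a PR, still a lost responder.

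**3. Which response categories use the baseline?**

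- CR requires stage 0 in every evaluable organ at the assessment, so it does not depend on the baseline.
- The VGPR criteria are absolute too, except for one alternative liver limb expressed as a fraction of the enrollment bilirubin.
- PR, mixed response and progression are defined by change, so a stale liver stage can alter them.

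**4. When does it reach ORR?** All four conditions must hold:

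- the waiver was used;
- no later predose bilirubin was recorded;
- bilirubin crossed a stage boundary between that draw and first dose;
- the liver decides whether the subject is a responder.

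The affected share is the product of these conditional probabilities. The documents give none of them.

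**5. Size, by assumption only.** One misclassified subject moves ORR by 1/70 = 1.4 points. Suppose a net share m of all subjects is misclassified in one direction. Replacing p by 0.40 + m or 0.60 − m in the step 1 formula gives:

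| m | Net subjects (70 × m) | P(success), true rate 40%, net false responders | P(success), true rate 60%, net lost responders |
|---|---|---|---|
| 0 | 0 | 0.0189 | 0.899 |
| 1% | 0.7 | 0.028 | 0.866 |
| 2% | 1.4 | 0.041 | 0.826 |
| 3% | 2.1 | 0.059 | 0.780 |
| 5% | 3.5 | 0.110 | 0.670 |

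The values of m are assumptions chosen to show sensitivity. Nothing in the documents says that m differs from zero, or in which direction.

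**The case against.** **The waiver is permissive.** Table 6 still schedules Day 1 chemistry, and Table 5 schedules Day 1 grading without any waiver. A careful site may infer that grading the liver needs a current bilirubin. That is fair, and it makes a stale baseline possible rather than certain. But nothing states that the grading duty overrides footnote b, and the SAP repeats the footnote.

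**A later result displaces the screening value.** SAP Section 4.1.3 takes the last value and covers unscheduled assessments, so any bilirubin recorded between screening and first dose becomes the baseline. This stands. It also weakens the argument from criterion 4a: where liver progression made the subject refractory, the bilirubin showing it already exists and, once recorded, is used. The gap is greater where skin or gut progression qualified the subject.

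**Stronger readings that the documents do not support.**

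- A reader might infer that Day 28 ORR and every later response endpoint are distorted. CR and most of VGPR are absolute. A subject whose skin or gut improved with no progression elsewhere is already a PR, so a false liver improvement changes nothing. The Day 14, 56 and 100 rates and the start of response for DOR are exposed only by the same narrow route.
- A reader might infer that the trial outcome hangs on this because 36/70 has an exact lower 95% limit of 39.2% and 37/70 has 40.6%. Those limits are correct, but any count threshold turns on one subject. At a true rate of 60%, exactly 36 of 70 has probability 3.3%. Neither figure measures this defect.
- A reader might extend the same fix to hematology. Stability is judged by the absence of a 50% or greater "decrease in platelet counts and/or ANC relative to Day 1" (Sections 5.2.1.1 and 5.4.2.2), and footnote b waives those Day 1 counts too. That reference governs dose escalation and plays no part in ORR. The passages need reconciling, but that is a separate matter.

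**Conclusion.** The gap is real and narrow. As written, both documents permit the liver baseline for response to be a bilirubin up to 7 days old, although response is defined against Study Day 1. Where the four conditions in the working hold, change before ruxolitinib is counted as response, mixed response or progression on drug.

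The conclusion rests on the text alone. The number of subjects affected, and whether false responders would outnumber lost ones, cannot be derived: the documents give no rate of liver involvement, waiver use or bilirubin change before first dose. The wording of the footnotes is certain, but a material effect on ORR is not shown. The change is worth making because it is cheap and protects the baseline of the primary endpoint in a study without a control arm.

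**What to change.** In Table 6 footnote b and SAP Appendix C footnote b, except total bilirubin from the waiver. Require a predose bilirubin at the Day 1 visit for every subject, and state that this value sets the Day 1 liver stage. The other analytes that do not feed liver staging can keep the 7-day allowance. The last-value rule in SAP Section 4.1.3 can remain as the fallback if the Day 1 result is missing.

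The cost is small. Chemistry is already scheduled on Day 1 and run at the local laboratory before dosing (Sections 7.5.6 and 7.5.6.1), and blood is already drawn predose that day for pharmacokinetics (Section 7.7.1). The burden is one local result for subjects whose site would have used the waiver. Sample size, decision boundaries and analysis methods do not change.

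Separately, the sponsor should reconcile footnote b with the Day 1 platelet and neutrophil reference in Sections 5.2.1.1 and 5.4.2.2. No rule is proposed here for that reference.

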6.1. Screening

The screening period is the interval between signing the ICF and the day that the subject is enrolled in the study (Day 1). The screening period may not exceed 28 days. Informed consent must be obtained before performing any study-specific procedures that are not considered standard of care. Assessments that are required to demonstrate eligibility may be performed over the course of 1 or more days during this period.

Procedures conducted as part of the subject's routine clinical management (eg, blood count, imaging study) and obtained before signing the ICF may be used for screening or baseline purposes, provided that the procedure meets the Protocol-defined criteria and has been performed in the timeframe of the study. Results from the screening visit evaluations will be reviewed to confirm subject eligibility before enrollment or the administration of study drug. Tests with results that fail eligibility requirements may be repeated once during the screening period if the investigator believes the results to be in error. For screening assessments that are repeated, the most recent available result before enrollment will be used to determine subject eligibility. Treatment should start as soon as possible, but within 2 days after the date of enrollment. Additionally, a subject who fails screening may repeat the screening process 1 time if the investigator believes that there has been a change in eligibility status (eg, following recovery from an infection).

6.2. Treatment

The treatment period begins on the day that the subject receives the first dose of study drug through the point at which the principal investigator determines that the subject will be permanently discontinued from the study drug. Dates for subsequent study visits will be determined based on this day and should occur within ± 2 days of the scheduled date unless delayed for safety reasons. During the Day 1 visit, results from screening visit evaluations should be reviewed to determine whether the subject continues to meet the eligibility requirements as specified in the Protocol.

6.3. End of Treatment

If a decision is made that the subject will permanently discontinue study treatment, then the EOT visit should be conducted. If the EOT visit coincides with a regular study visit, then the EOT evaluations will supersede those of that scheduled visit, and the data should be entered in the EOT visit in the eCRF. The subject should be encouraged to return for the follow-up visit.

6.4. Follow-Up

6.4.1. Safety Follow-Up

The safety follow-up period is the interval between the EOT visit and the scheduled follow-up visit, which should occur 30 to 35 days after the EOT visit (or after the last dose of study drug if the EOT visit was not performed). Adverse events and SAEs must be reported up until at least 30 after the last dose of study drug, the date of the follow-up visit, or until toxicities resolve, return to baseline, or are deemed irreversible, whichever is longer.

6.4.2. GVHD Assessment Follow-Up

Subjects who discontinue study treatment for reasons other than progression of GVHD will move into the disease status follow-up period and should be assessed every 28 days to monitor disease status. Every effort should be made to collect information regarding disease status until one of the following occurs:

- GVHD progression
- Relapse of malignancy
- Death
- End of study

